8.2 REPEATED OR UNSCHEDULED ASSESSMENTS OF SAFETY PARAMETERS

If a patient has repeated safety assessments (e.g., for a lab endpoint) prior to initial dosing of study drug, then the results from the final non-missing assessment made prior to the start of study drug will be used as baseline. If there is more than 1 safety measurement (e.g., for a lab endpoint) at a postbaseline timepoint, only the last measurement will be used. All postbaseline assessments including unscheduled assessments, if any, will be used for PCS value determination, and all assessments will be presented in by-patient listings.

8.3 CONVENTIONS FOR SUMMARIZING ADVERSE EVENTS

The following conventions will be followed in summarizing TEAEs within a treatment group:

- For patient incidence summaries, each patient will be counted only once within each SOC, PT, or the overall AE summary
- If a patient reported more than 1 AE within an SOC or PT, then the AE with the highest severity or strongest causality relationship to study drug per investigator within each SOC and each PT will be included in the respective summaries by severity or relationship, respectively.

8.4 MISSING DATE INFORMATION FOR ADVERSE EVENTS

If the onset date of an AE is missing / incomplete, it is assumed to have occurred during the study (i.e., a TEAE) except if the partial onset date or other data, such as stop date, indicates differently.

8.5 MISSING SEVERITY ASSESSMENT FOR ADVERSE EVENTS

If severity is missing for an AE that started prior to initiation of study drug dosing, all efforts should be made to obtain the severity from the Investigator. If it is still missing after all efforts, then a severity of “Mild” will be assigned. If the severity is missing for a TEAE, then a severity of “Severe” will be assigned. The imputed values for the missing severity assessment will be used for the incidence summary, while the actual missing values will be presented in by-patient listings.

8.6 MISSING RELATIONSHIP TO STUDY DRUG FOR ADVERSE EVENTS

If the relationship to study drug is missing for a TEAE, all efforts should be made to obtain the relationship from the Investigator. If it is still missing after all efforts, a study drug causality of “Related” will be assigned in the corresponding analysis-derived data set for non-serious and non-AECI treatment-emergent adverse events. The imputed values for the missing relationship to study drug will be used only for incidence summary, while the actual missing values will be presented in by-patient data listings. For SAEs and AECIs, if causality from investigators is missing after all efforts to obtain it, then the causality determination from the sponsor will apply.

8.7 MISSING DATE INFORMATION FOR PRIOR OR CONCOMITANT MEDICATIONS

If the onset date of a medication is missing / incomplete, it is assumed to have occurred during the study (i.e., concomitant) except if the partial onset date or other data, such as stop date, indicates differently).

10. APPENDIX 1 – ADVERSE EVENTS OF CLINICAL INTEREST

The table below provides the criteria for identifying adverse events within each category. Medical review of AEs prior to database lock will identify any additional adverse events.

Table 8. Criteria for AECI

Event Category	AE Criteria	Labs/Vital Sign
Bleeding Events	Identify using MedDRA SMQ of 'haemorrhage terms (excluding laboratory terms)'	
Hypotensive Events	Identify using the following MedDRA preferred terms: Blood pressure ambulatory decreased Blood pressure decreased Blood pressure diastolic decreased Blood pressure systolic decreased Blood pressure orthostatic decreased Orthostatic hypotension Presyncope Syncope Dizziness Dizziness postural	Decrease in SBP >20 mmHg from seated to standing Decrease in DBP >15 mmHg from seated to standing
Elevated Heart Rate	Identify using the following MedDRA preferred terms: Heart rate increased Orthostatic heart rate increased Tachycardia Palpitations	Increase in pulse >30 bpm from seated to standing
Headaches	Identify using MedDRA HLGT Headache	

SMQ=standardised MedDRA query.

11.

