3.4 STUDY SCHEMATIC AND SCHEDULE OF ASSESSMENTS

The schedule of evaluations for Study C1973-204 is presented in Table 2.

Table 2. Schedule of Events

	Screening Period			Treatment Period				FU Period
	Screening Visit* (Day -45 to -3)	Baseline*Visit (Day -14 to -3)	Randomization Visit (Day 1)	Week 2 Visit (Day 15±3)	Week 4 Visit (Day 29±3)	Week 8 Visit (Day 57±3)	Week 12/ EOT Visit (Day 85 -7/+4)	
Visit Days →								
Study Procedure ↓								
ICF signed	X							
Demographics	X							
Medical history	X							
Inclusion/exclusion	X	X	X					
Prior & concomitant medications and procedures	X	X	X	X	X	X	X	
Physical exam (a)	complete	pre CPET	predose	predose	predose	predose	predose	complete
Vital signs (BP, pulse, RR, & oral temperature) (b)	X	pre CPET	pre: 0 (≤1h) pd: 1,3,4h (±20m)	pre: 0 (≤1h) pd: 1,3,4h (±20m)	pre: 0 (≤1h)	pre: 0 (≤1h)	pre: 0 (≤1h)	X
Weight, height	W, H	W	W	W	W	W	W	W
NYHA classification	X		X				X	X
Hepatitis, HIV screen	X							
Urine drug screen	X							
Urine pregnancy (c)	X	pre CPET	predose	predose	predose	predose	predose	X
Urinalysis sample (d)	X		predose	predose	predose	predose	predose	X
Serum chemistry, CBC, coagulation (d)	X	pre CPET	predose	predose	predose	predose	predose	X
Hemoglobin A1c	X	pre CPET						
12-lead ECG (e)	X	pre CPET	predose	predose	predose	predose	predose	X
Adverse events	X	X	X	X	X	X	X	X
CPET (f)		X					postdose >1h (or ±3 days) (f)	
6MWT (g)			post CPET >1h				post CPET >1h (g)	post CPET >1h
NT-proBNP sample (d,h)	X (if needed)	pre CPET						
Echocardiography (i)	X (if needed)		X (for baseline)				predose	X

	Screening Period			Treatment Period				FU Period
	Screening Visit* (Day -45 to -3)	Baseline*Visit (Day -14 to -3)	Randomization Visit (Day 1)	Week 2 Visit (Day 15 ±3)	Week 4 Visit (Day 29 ±3)	Week 8 Visit (Day 57 ±3)	Week 12/ EOT Visit (Day 85 -7/+4)	
Visit Days → Study Procedure ↓								
Fasting plasma glucose & insulin (d)		pre CPET	predose					
UACR sample supplies dispensed		X						
First-void urine samples (j)			preVisit					
Pharmacokinetic blood samples			predose pd:1,2,4h (±20m)	predose pd:1,2,4h (±20m)	predose	predose	predose pd:1,2,4h (±20m)	X
Orthostatic (sitting to standing) pulse, BP (k)			pre: 0 (≤1h) pd: 2,4h (±20m)	pre: 0 (≤1h) pd: 2,4h (±20m)			pre: 0 (≤1h)	
Randomization			X					
Study drug dispensed			X	X	X	X		
In-clinic study drug (l)			X	X	X	X		
Study drug return			X	X	X	X		
Study completion			X				X	

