6.9.2 Adverse Events

An overall summary table of all adverse events will be presented and include the following:

- Patients with any TEAEs,
- Patients with any TEAEs by maximum severity,
- Patients with any TEAEs related to the Investigational Medicinal Product (IMP),
- Patients with any TEAEs leading to drug withdrawn,
- Patients with any SAEs,
- Patients with any TEAEs of Clinical Interest (AECIs; see Section 6.9.2.2).

All TEAEs will be summarized for each treatment group with the number and percentage of subjects by SOC and PT; by relationship to study drug, by maximum severity. If a patient has more than 1 TEAE coded to the same preferred term, the patient will be counted only once for that preferred term by identifying those TEAEs with the highest severity (severe > moderate > mild) and the strongest causality relationship (related > not related) to study drug per investigator.

AEs will also be summarized by study period, where AEs that started during the Screening Period, Treatment Period or Follow-up Period will be presented by treatment group (placebo and 40 mg pralicipat only) for the respective period.

For presentation of AE incidence, AEs will be sorted alphabetically by SOC, and within each SOC, by decreasing incidence of PT in the pralicipat 40 mg group. An additional presentation will include a summary of TEAEs for each treatment group by PTs only, sorted by decreasing incidence of PT in the pralicipat 40 mg group.

Summary tables will also be presented for SAEs in decreasing overall PT frequency.

Listings of AEs in screen failure patients, pretreatment AEs in randomized patients, TEAEs, severe TEAEs, study drug-related TEAEs, SAEs, TEAEs leading to study discontinuation and AEs leading to death (if any) will be provided. The listings will include the dose levels that the patients are using when AEs occur.

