6.9.2.2 TEAEs of Clinical Interest (AECI)

Although not collected as such in the protocol, based on a possible class effect with sGC stimulators, TEAEs related to bleeding, hypotension, and elevated heart rate will be categorized as AECI. These will be summarized by treatment group, by severity and by PT and presented in

a by-patient listing. See Appendix 1 for details on the determination of the events for each category of interest.

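### The preferred-term list for hypotensive adverse events of clinical interest leaves out 'Hypotension' itself, so such events enter the summary only if a medical review with no stated criteria adds them

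*SAP*

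**What the plan says.** SAP 6.9.2.2 sets the categories: "TEAEs related to bleeding, hypotension, and elevated heart rate will be categorized as AECI". The reason given is a possible class effect of sGC stimulators. Appendix 1 is cited for how events are assigned.

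In Appendix 1, Table 8, the Hypotensive Events row works from named MedDRA preferred terms. Nine of them read "Blood pressure ambulatory decreased Blood pressure decreased Blood pressure diastolic decreased Blood pressure systolic decreased Blood pressure orthostatic decreased Orthostatic hypotension Presyncope Syncope Dizziness"; the tenth is postural dizziness. The vital-sign column of that row gives "Decrease in SBP >20 mmHg from seated to standing Decrease in DBP >15 mmHg from seated to standing".

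Above the table stands the only open-ended provision: "Medical review of AEs prior to database lock will identify any additional adverse events".

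AECI status is used in two other places. The overall adverse event table in SAP 6.9.2 has a row for patients with any AECI. SAP 8.6 handles missing causality differently for AECIs and for other events.

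**The concern.** The category is hypotension, but the list that identifies it does not contain that word as a term of its own. The omission does not look like a choice of scope. A narrow definition would hardly include non-specific dizziness, and a broad one would hardly leave out the central term.

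Hypotension is one of three effects named in SAP 6.9.2.2, and one of the two serious-event categories in Protocol Table 5. A reader of the study report will take the hypotension AECI line as the count of hypotension events. As specified, that line would count a patient with dizziness and could omit a patient whose event was coded as hypotension.

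**Working it through.** The plan gives no figure to reproduce. The check is whether any stated rule brings the term into the category.

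**1. The list.** The ten terms fall into three groups:
- five blood-pressure-decreased terms: ambulatory, unqualified, diastolic, systolic and orthostatic
- one diagnosis term, orthostatic hypotension
- four symptom terms: presyncope, syncope, dizziness and postural dizziness

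Plain 'Hypotension' appears 0 times in 10.

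**2. The comparable row.** Elevated Heart Rate is also a hand-built list: "Heart rate increased Orthostatic heart rate increased Tachycardia Palpitations". It has both a measurement term and the unqualified diagnosis, tachycardia. The hypotension row has the measurement terms but only the orthostatic form of the diagnosis.

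**3. Other routes into the category.**
- *Grouped queries.* Bleeding uses a standardised MedDRA query and Headaches a high-level group term. The hypotension row has neither.
- *Vital signs in Table 8.* Both criteria are falls on standing, so a low seated pressure without such a fall does not meet them. The SAP schedule (Table 2), as printed, has orthostatic pressure at three visits only. Table 8 also does not say whether these criteria add to the terms or must accompany them.
- *Seated pressure in SAP 6.9.4, Table 6.* This feeds a separate table of potentially clinically significant values, not the AECI summary.
- *Medical review.* The timing is stated (before lock). No criteria are given, nor any rule that a term added for one patient applies to all patients with it.

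Only the last route remains.

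**4. Where a missed event would and would not matter.**
- Affected: the hypotension AECI summary and listing, and the any-AECI row in SAP 6.9.2.
- Affected in rare cases: causality. Under SAP 8.6 a missing relationship is set to related, and this value "will be assigned in the corresponding analysis-derived data set for non-serious and non-AECI treatment-emergent adverse events". For an AECI the sponsor's determination applies instead. A missed non-serious event with missing causality would therefore default to related.
- Unaffected: the count of patients with any TEAE (SAP 6.9.1) and the tables by system organ class and preferred term (SAP 6.9.2).
- Unaffected: individual stopping criteria and DMC reviews, which rest on the serious events in Protocol Table 5 (Protocol 3.7 and 5.13).

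**5. Scale.** SAP 4 plans 184 patients and assumes 10% were randomized to 10 or 20 mg.
- Two main arms: 184 × 0.90 = 165.6, or 165.6 / 2 = 82.8 per arm.
- One missed patient: 1 / 82.8 = 1.21 percentage points of that arm's incidence.
- If all 184 were in the two arms: 1 / 92 = 1.09 percentage points.

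Let p₁ and p₀ be the true incidences, and suppose a share m is missed in both arms. The expected ratio is p₁(1 − m) / [p₀(1 − m)] = p₁ / p₀, which is unchanged. The expected difference is (1 − m)(p₁ − p₀), which is smaller by the share m.

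**The case against.** The strongest reply is that the list is not closed. The medical review is there to add events, SAP 6.9.2.2 fixes the category, and reviewers would have to pass over an event bearing the category's own name. The review comes before lock while the study team is blinded (SAP 3.3), so it cannot select events by treatment. All of this stands, and the under-count may be zero. But completeness then rests on a judgement with no written criteria, for a term that the list could simply name.

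Marked low seated pressure is also reported by arm through Table 6 of SAP 6.9.4, with a listing of the adverse events of those patients. The preferred-term table would show hypotension directly. Both points limit the harm, but neither corrects the AECI line.

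The causality effect needs several coincidences, and its default of related is conservative: it cannot understate drug-related events. That is right, and it is a minor strand.

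Finally, the documents do not reproduce the MedDRA hierarchy, so it is an inference that 'Hypotension' is a codable preferred term. A line lost from the table when the PDF was read cannot be fully excluded either, although the list shows no gap or redaction mark. The mismatch between the category name and the list does not depend on the inference; the exact wording of the fix does.

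**Conclusion.** The concern holds. The identification rule in Table 8 does not match the category it serves, and no other stated rule closes the gap. The effect is modest and confined to a descriptive safety summary. It is a possible under-count of hypotension AECIs and of patients with any AECI, with a rare side effect on missing causality.

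The size cannot be derived, because the documents give no adverse event rates. It ranges upward from zero, at about 1.1 to 1.2 percentage points of an arm's incidence for each patient missed. That scale assumes the planned 184 patients, with either 10% or none of them in the discontinued dose groups. The conclusion also assumes that the Table 8 list is complete as printed and that 'Hypotension' can be coded as a term of its own. The latter is inferred from the category name and the listed orthostatic variant. The change should be made, but nothing in the primary analyses depends on it.

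**What to change.** In SAP Appendix 1, Table 8:
- Add 'Hypotension' to the Hypotensive Events term list.
- Re-check the list against the coded adverse event terms before database lock and unblinding.
- State that any preferred term the medical review adds applies to every patient with that term.

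The cost is one term, one sentence and one check of coded terms. No new data, visits or patients are needed.

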APPENDIX 2 – [REDACTED]

12.

APPENDIX 3 – [REDACTED]

13. APPENDIX 4 – POOLING OF TRIAL CENTERS

Because of the potential of many trial centers to have a small number of patients, the centers will be pooled by the following 6 geographic regions (as listed in Table 10): Northeast, Southeast, Midwest, Southwest, and West. Analyses using geographic region will use this 6-category geographic region variable.

Table 10. Definition of Geographic Regions

Northeast	Southeast	Midwest	Southwest	West	Ex-US
CT	AL	IA	AZ	CA	Canada
DC	AR	IL	NM	CO	
DE	FL	IN	OK	ID	
MA	GA	KS	TX	MT	
MD	KY	MI		NV	
ME	LA	MN		OR	
NH	MS	MO		UT	
NJ	NC	ND		WA	
NY	SC	NE		WY	
PA	TN	OH			
RI	VA	SD			
VT	WV	WI			

14.

APPENDIX 5
